10.8.2 ADVERSE EVENTS

AEs will be coded using the latest version of MedDRA. The analysis of AEs will include descriptive statistics and will be summarized through the use of frequency tables overall and by type (AE or serious adverse event [SAE]) SOC and PT, intensity, and relationship of events to treatment. Summaries for adverse events will include number of subjects as well as number of events.

A treatment-emergent adverse event (TEAE) is defined as an AE that occurs or worsens after the first study drug administration. AEs having both onset and end dates missing will be considered as TEAEs. AEs having missing onset date and not missing end date AE will be considered as TEAE unless end date is prior to the date of the first dose.

Related AEs are AEs with missing, probably related, possibly related, and definitely related relationship to study drug.

An overall summary of AEs will include the number of subjects who experienced at least one AE of the following categories: any TEAE; any SAE; any related TEAE, any TEAE leading to early study termination; and any TEAE leading to death.

The incidence of TEAEs will be summarized by SOC and PT; by SOC, PT and intensity; and by

SOC, PT and relatedness. If the same AE (based on SOC and PT) is reported for the same subject more than once, the AE is counted only once for that SOC and PT, and at the highest intensity or relatedness, respectively.

In addition, the incidence of SAEs and TEAEs leading to early study termination will be presented by SOC and PT. If the same AE (based on SOC and PT) is reported for the same subject more than once, the AE is counted only once for that SOC and PT.

Separate listings will be prepared for all AEs, SAEs, AEs leading to early study termination, and AEs leading to death.

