⁴ Thrombogenicity marker assessments at 15-30 minutes, 4-6 hours and 24-26 hours post-infusion of PK dose.

⁵ Includes hemoglobin, hematocrit, absolute counts of: white blood cells, neutrophils, monocytes, lymphocytes, eosinophils, basophils, platelets and red blood cells; mean platelet volume (MPV), mean corpuscular volume (MCV), mean corpuscular hemoglobin (MCH) and mean corpuscular hemoglobin concentration (MCHC) to be assessed at a local laboratory.

⁶ Includes ALT, AST, ALP, BUN or urea, uric acid, creatinine, total bilirubin and glucose to be assessed at a local laboratory.

⁷ Urine dipstick, followed by microscopy if abnormal to be assessed at a local laboratory.

⁸ Investigator's efficacy assessment and review of subject's diary including infusions, bleeding summary, subject's efficacy assessment, adverse events and concomitant medications. At Screening, review of subject diary to include review of previous factor IX therapy (if available).

⁹ Inhibitory and non-inhibitory factor IX antibodies to be assessed by central lab at PK Phase Pre-infusion for subjects weighing ≥ 28 kg, and all subjects at all other time points.

¹⁰ Factor IX mutation assessment to include mutation genotyping by central laboratory if not previously documented. For patients below 10 kg this may be done at any time during the study when blood volumes allow

¹¹ Factor IX activity to be assessed by central lab pre-infusion and post-infusion at 15-30 minutes, 4-6 hours, 24-26 hours, and 46-50 hours. Pre-infusion and 15 to 30 minutes post-infusion samples will be tested for factor IX activity to determine the starting prophylaxis dose. See section [5.7.1](#) for further details.

¹² Screening to occur 21 to 5 days prior to PK phase.

¹³ CD4 count to be assessed by local laboratory.

¹⁴ See [Table 2](#) for thrombogenicity assessments by subject weight; thrombogenicity markers include D-dimer, TAT complex, fragment 1+2.

¹⁵ For patients below 17 kg, CBC with differential and serum chemistry should be collected if blood volumes allow.

¹⁶ Anti-CHOP antibodies to be assessed by central laboratory at PK phase pre-infusion for subjects weighing ≥ 28 kg

Table 2: Thrombogenicity Assessments During PK Phase by Subject Weight

Subject weight	Pre-infusion	15-30 min post-infusion	4-6 hours post-infusion	24-26 hours post-infusion
≥ 20 kg	X	X	X	X
≥ 17 kg to <20kg	X	X		X
< 17 kg ¹				

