4.2.3. Subject Replacement

Subjects withdrawn from the trial or who withdraw consent prior to dosing will be replaced. Subjects withdrawn from the trial or who withdraw consent after dosing may be replaced.

Subjects are eligible to be rescreened for a screening failure only if the patient was unable to be enrolled during the screening period due to scheduling issues or due to bleeding. Subjects may be rescreened up to 3 times for these reasons.

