9.1.1. Definition of an Adverse Event

An adverse event (AE) is defined as any untoward, undesirable, or unintended medical occurrence in a clinical trial subject administered APVO101 which does not necessarily have a causal relationship with APVO101. For purposes of this clinical trial, an AE can therefore be any unfavorable and unintended sign (e.g., including an abnormal laboratory finding), symptom, or disease temporally associated with the use of APVO101, whether or not related to the product.

Examples of an AE include:

- Exacerbation of a chronic or intermittent pre-existing condition, including either an increase in frequency or intensity of the condition
- Significant or unexpected worsening or exacerbation of the condition/indication under study (hemophilia B)
- A new condition detected or diagnosed after study product administration even though it may have been present prior to the start of the study
- Signs, symptoms, or clinical sequelae of a suspected overdose of either study product or a concurrent medication (“overdose” per se, should not be reported as an AE)
- Pre- or post-treatment events that occur as a result of protocol-mandated procedures (e.g., invasive protocol-defined procedures, modification of a subject’s previous drug treatment regimen)
- A sub-optimal response to APVO101 treatment observed in two separate bleeding episodes in the same subject over the course of the study; although, the investigator will have the option of reporting a sub-optimal response to one bleed as an AE.
- A thromboembolic event (TEE)
- Nephrotic syndrome
- Hypersensitivity reaction, allergic reaction, anaphylaxis, anaphylactic shock; including, but not limited to symptoms of difficulty breathing, shortness of breath, swelling, hives, generalized urticaria, tightness of the chest, bronchospasm, laryngospasm, wheezing, hypotension, blurred vision
- Severe anaphylaxis; symptoms may include severe hives, severe swelling, severe chest tightness, difficulty breathing, wheezing, faintness, rapid heart rate, and low blood pressure

An AE **does not** include:

- Medical or surgical procedures (e.g., colonoscopy or biopsy); the medical condition that leads to the procedure is an AE
- Social or convenience hospital admissions where an untoward medical occurrence did not occur
- Day-to-day fluctuations of a pre-existing disease or conditions present or detected at the start of the study that do not worsen

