- The disease/disorder being studied (hemophilia B), or expected progression, signs, or symptoms of the disease/disorder being studied (e.g., bleeding episodes) unless more severe than expected for the subject's condition

All AEs that occur after informed consent/assent is signed will be recorded in the source documents and on the appropriate CRF page.

In addition, all hypersensitivity and allergic reactions, anaphylaxis, and/or anaphylactic shock reactions will be recorded on the APVO101 Hypersensitivity Reaction Reporting Form; this form will be transmitted to Medexus Pharmacovigilance within 24 hours of the occurrence using the contact information below:

[REDACTED]

The information to be collected includes the nature, date and time of onset, intensity, duration, causality, and outcome of the event. Even if the AE is assessed by the investigator as not reasonably attributable to APVO101, its occurrence must be recorded in the source documents and on the appropriate page of the CRF.

Treatment-emergent AEs will be defined as AEs that occur after the first infusion with APVO101.

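### SAP 10.8.2 does not limit the SAE counts to treatment-emergent events, so a serious event between consent and first infusion in a child who is later dosed would be tabulated with on-treatment SAEs

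*SAP*

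**What the plan says.** SAP 10.8.2 defines treatment emergence: "A treatment-emergent adverse event (TEAE) is defined as an AE that occurs or worsens after the first study drug administration". It then sets out five categories for the overall summary: "any TEAE; any SAE; any related TEAE, any TEAE leading to early study termination; and any TEAE leading to death". For the tables by system organ class (SOC) and preferred term (PT), it says that "the incidence of SAEs and TEAEs leading to early study termination will be presented by SOC and PT". In both places the treatment-emergent limit is attached to the neighbouring items but not to the SAEs. The same section plans separate listings, including one of all SAEs.

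On collection, Protocol 9.1.1 states: "All AEs that occur after informed consent/assent is signed will be recorded in the source documents and on the appropriate CRF page". Its examples of adverse events include "Pre- or post-treatment events that occur as a result of protocol-mandated procedures", and modification of the previous drug regimen is given as one such procedure. Protocol Table 1 has adverse events assessed at Screening, with the timing "Screening to occur 21 to 5 days prior to PK phase". Protocol 5.7.1 requires a washout of previous factor IX before the PK dose, which is the first APVO101 infusion.

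SAP 9 defines the Safety population as everyone who received at least one dose, and SAP 10.8 uses it for all safety outcomes.

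**The concern.** The SAE row and the SAE table will be read as a description of what happened on APVO101, particularly because every other row of the overall summary is treatment-emergent. If they can also hold events from screening or washout, the SAE count mixes two things: what happened after exposure, and what happened before any exposure, possibly because prior therapy was interrupted for the trial.

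Safety is the first primary objective. Under SAP 11 the same summaries go into the interim analysis for the integrated pediatric report that meets the US post-marketing requirement. With at most 22 children, a single event is visible in the percentage.

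**Working it through.** The plan states no SAE rate, power or target precision, so there is no figure of its own to reproduce. The check is whether any rule in the text keeps a pre-dose SAE out of the tables, and then how much one event would move them.

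**Does any rule exclude a pre-dose SAE in a child who is later dosed?**

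1. Collection starts at consent (Protocol 9.1.1), so the event is in the database.
2. Pre-treatment events caused by protocol-mandated procedures are named as adverse events (Protocol 9.1.1), and the washout is mandated (Protocol 5.7.1). An event of this kind is therefore not ruled out by type.
3. The Safety population (SAP 9) filters persons. A child who is later dosed is in it, whatever the date of the event.
4. The treatment-emergent definition in SAP 10.8.2 would filter by date, and SAP 10.3.1 supplies imputation rules for that classification. Neither is applied to the SAE category or to the SOC/PT table of SAEs.
5. No other text in the two documents limits the SAE tables to events after the first infusion. The table shells are in a separate document (SAP 14) that is not available here.

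So the rule as written counts the event.

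**How much does one event move the table?**

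The change for one affected child with no other SAE is 1/n.

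| Denominator | Source | With the event | Treatment-emergent only |
|---|---|---|---|
| 22 | maximum enrolment, SAP 7 | 1/22 = 4.5% | 0/22 = 0% |
| 20 | upper end of evaluable target, SAP 7 | 1/20 = 5.0% | 0% |
| 15 | lower end of evaluable target, SAP 7 | 1/15 = 6.7% | 0% |
| 10 | target per age group, Protocol 3.3; split by age, SAP 10.1 | 1/10 = 10.0% | 0% |

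**How likely is such an event?**

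The documents do not say. As an assumption only, let p be the chance that a child who is later dosed has a pre-dose SAE. The chance of at least one among 22 is 1 − (1 − p)^22:

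- p = 0.5%: 10.4%
- p = 1%: 19.8%
- p = 2%: 35.9%
- p = 5%: 67.6%

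The exposed time is short. At 21 days per child it is 22 × 21 = 462 child-days, about 1.3 child-years. With the expected participation of at least 12 months (Protocol 3.1), this is at most about 21/(365 + 21) = 5% of observed time. Rescreening could lengthen it. Nothing in the documents shows where in the range of p the trial lies.

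**The case against.** The case for leaving the text alone has several parts.

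- **Counting every SAE in dosed children is conservative, and the row says what it is.** This stands as a defence against any charge of concealment. A reader might infer that the summary contradicts itself because the SAE row need not be a subset of the treatment-emergent row. It does not: no planned row reports SAEs within treatment-emergent events, so no two entries conflict. But a separate pre-dose row keeps every event visible and also says when it happened, so nothing conservative is lost.
- **The definitions may already exclude pre-dose events.** Protocol 9.1.2 words an SAE as a response at a dose, and Protocol 9.1.1 speaks of a subject given APVO101. That is a possible reading. The same Protocol 9.1.1 lists pre-treatment events and collects from consent, and the SAP never uses the dose wording as a filter. The text is ambiguous, which is a reason to settle it.
- **Pre-dose SAEs will be rare.** Protocol 4.2.3 allows rescreening of children "unable to be enrolled during the screening period due to scheduling issues or due to bleeding", and a reader might take this as showing that pre-dose SAEs are expected. It does not. Under Protocol 9.1.1 a bleed is an adverse event only if more severe than expected for the child's condition, and it must then also meet a seriousness criterion. Hospitalization planned before inclusion is not an SAE (Protocol 9.1.2), and an SAE in a screen failure who is never dosed falls outside the Safety population. This part of the objection stands.
- **The listing already resolves it.** With at most 22 children, a reader can compare each onset date with the first infusion. True, but the tabulated count is what an integrated report carries forward.
- **The shells may carry the limit.** They may. The SAP text should govern them.

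**Conclusion.** The gap in wording is real and small. As written, SAP 10.8.2 would count an SAE between consent and first infusion with on-treatment SAEs, provided the child is later dosed. One event is worth 4.5 percentage points at n = 22, or 10 points in an age group of 10, when the child has no other SAE.

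Two stronger conclusions are not supported. A reader might calculate exact 95% limits and say that the interval shifts from 0–15.4% to 0.1–22.8% at n = 22. No such interval would be reported: Protocol 11.4.3 plans exact intervals only for the incidence of non-inhibitory factor IX antibodies and anti-CHOP antibodies, and SAEs get frequency tables. A reader might also infer that the safety evaluation as a whole is contaminated. The related, early-termination and death categories of the overall summary are already treatment-emergent, and all SAEs are listed.

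The conclusion assumes that the shells add no date filter, that Protocol 9.1.2 is not applied as one, and that such an event occurs at all. The bleeding rate, PK and immunogenicity results do not depend on it.

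**What to change.** In SAP 10.8.2, change the SAE category of the overall summary and the SOC/PT table to treatment-emergent SAEs, using the definition in that section and the date rules in SAP 10.3.1 and 10.8.2. An event that starts before the first infusion and worsens afterwards stays treatment-emergent under that definition, and one with no dates at all is treated the same way.

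Add one row to the overall summary for SAEs from consent to first infusion that are not treatment-emergent, in the Safety population, and flag these events in the SAE listing already planned. Bring the table shells into line, and apply the same rows to the interim summaries under SAP 11.

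The cost is a few words in the SAP, one table row and one flag. No new data are needed and no event drops out of the report.

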10.8.4 VITAL SIGNS AND OTHER SAFETY PARAMETERS

10.8.4.1 VITAL SIGNS

Descriptive statistics of vital signs (temperature [degree C], systolic and diastolic blood pressure [mmHg], pulse rate [beats per minute; bpm] and respiratory rate [breaths/min]) at each scheduled visit, as well as the change from baseline will be presented. Summary will be prepared for all assessments excluding those made during surgery. Data collected during surgery will be listed.

All vital signs data will be presented in a by-subject listing.

10.8.4.2 BLEEDING EPISODES

Bleeding episode location, cause and side of bleed will be summarized on by-episode level cumulative at 50ED and 100ED.

10.8.4.3 PHYSICAL EXAMINATION

Listing of physical examination findings will be provided by subject.

10.9 OTHER ENDPOINTS AND ANALYSIS

10.9.1 GENOTYPES

Mutation genotypes of subjects whose mutations are known at screening and those who undergo genotyping during the study will be listed. The available genotypes are:

- Missense
- Nonsense
- Synonymous
- Large structure change (>50 base pairs [bp])
- Small structure change (in-frame, <50bp)
- Frameshift
- Promoter
- Splice site change

11. INTERIM ANALYSIS

When a sufficient number of subjects completes their 50 ED visit, available PK and safety/efficacy data (for at least 50 ED) will be included for data analysis of an integrated pediatric report for United States post-marketing requirement.

The summaries presenting all efficacy, safety, and PK endpoints listed in Section 10 will be included into interim analysis.

All data collected in the study by the time of interim analysis will be listed.

12. DEVIATIONS FROM ANALYSIS AS DESCRIBED IN THE PROTOCOL

Protocol version 3.0 amendment 2.0 section 11.4.2. 'Efficacy analysis specifies:

The annualized bleeding rate will be calculated and summarized, including the median, interquartile range and the 95% exact confidence interval for the median, assuming that the rates follow a Poisson distribution.

Sponsor confirmed that the wrong word has been used in this statement due to oversight. 95% confidence intervals are planned to be derived for mean (not median), analyzed in the same manner as the previous IB1001 studies.

Additional analysis of normalized (square-root transformed) ABR was also added to the efficacy

analysis to provide data comparable to results from studies IB1001-01 and IB1001-02.

According to the protocol, efficacy endpoints are evaluated for the Treatment and Continuation phases of the study (section 11.2.2). The Treatment phase begins after PK phase assessments are completed (section 5.7). The sponsor clarified that the evaluation of APVO101 efficacy with respect to prevention of breakthrough bleeding and with respect to control of hemorrhaging in pediatric patients, should be assessed after the initial infusion of APVO101 (PK phase) as this first infusion of 75 IU/kg is intended to protect subjects prophylactically. Therefore, any bleeding episode that occurs during the PK phase, will be evaluated and considered as belonging to the Treatment phase.

13. PROGRAMMING SPECIFICATIONS

All outputs will be produced using SAS version 9.4 or a later version.

The margins should be at least 1.50 inches for the binding edge and 1.0 inches for all others.

In the top left portion of each output the protocol number and deliverable type will be presented. In the top right the company name and page number will be presented. In the next line 3 lines, centre-adjusted the table/listing number, title and population information will be displayed. Footnotes will be placed under the main body at the bottom of the page. There should be one blank line between table content and the footnotes. The SAS program name and its location and creation date will appear bottom left. The source listing number or analysis data set name will appear on the bottom left corner of each output. The database cut-off/database lock date along with outputs status (Draft/Final) will appear just below the source listing.

Tables and listings (no figures are planned in the study) will be provided to Sponsor as two .pdf files each of them containing all tables and all listings. In addition the same files as .docx files will be provided to PSI medical writing to facilitate CSR writing.

14. LIST OF TABLES AND LISTINGS

Shells for tables and listings are provided in a separate mock-up TLs document.

15. APPENDIX I. SCHEDULE OF ASSESSMENTS

Evaluations	Screening ¹²	PK Phase		Treatment Phase				Continuation Phase			End of Study or Early Termination
				5 ED (±1 ED)	12 ED (±2 ED)	25 ED (±3 ED)	50 ED (±5 ED)	75 ED (±5 ED)	100 ED (±5 ED)	Every 3 months (~25 ED ± 5 ED)	
Informed consent and/or assent	X										
Eligibility Criteria Review	X										
Medical and hemophilia-related history	X	X									
Demographics (age, sex)	X										
Factor IX mutation assessment					X ¹⁰						
Concomitant medications	X	X		X	X	X	X	X	X	X	X
Physical exam, body weight and height	X	X				X	X	X	X	X	X
Vital signs	X	X	X ³			X	X	X	X	X	X
Thrombogenic markers ¹⁴		X ¹⁴	X ^{4,14}								
CBC with differential ⁵	X				X ¹⁵	X ¹⁵	X ¹⁵	X ¹⁵	X ¹⁵	X ¹⁵	X ¹⁵
CD4 count ¹³	X										
Serum chemistry ⁶	X				X ¹⁵	X ¹⁵	X ¹⁵	X ¹⁵	X ¹⁵	X ¹⁵	X ¹⁵
Inhibitor titer and non-inhibitory factor IX binding antibodies ⁹	X	X ⁹		X	X	X	X	X	X	X	X

	Screening ¹²	PK Phase		Treatment Phase				Continuation Phase			End of Study or Early Termination
				5 ED (±1 ED)	12 ED (±2 ED)	25 ED (±3 ED)	50 ED (±5 ED)	75 ED (±5 ED)	100 ED (±5 ED)	Every 3 months (~25 ED ±5 ED)	
Evaluations		Pre-infusion ¹	Post-infusion ²								
Anti-CHOP antibodies	X	X ¹⁶		X	X	X	X	X	X	X	X
Assessment of major and/or target joints	X						X		X		X
Urinalysis ⁷	X					X	X	X	X	X	X
Factor IX activity ¹¹		X	X								
Adverse events	X		X	X	X	X	X	X	X	X	X
Efficacy/subject diary ⁸	X			X	X	X	X	X	X	X	X
Training on subject diary and APVO101 reconstitution and administration	X										

¹ From 2 hours to 15 minutes pre-infusion.² At 15-30 minutes, 4-6 hours, 24-26 hours and 46-50 hours post-infusion of 75 ± 5 IU/kg (PK dose).³ Vital signs (pulse rate, blood pressure, respiratory rate and temperature) at 15-30 minutes, 4-6 hours, 24-26 hours and 46-50 hours post-infusion of PK dose.⁴ Thrombogenicity marker assessments at 15-30 minutes, 4-6 hours and 24-26 hours post-infusion of PK dose.⁵ Includes hemoglobin, hematocrit, absolute counts of: white blood cells, neutrophils, monocytes, lymphocytes, eosinophils, basophils, platelets and red blood cells; mean platelet volume (MPV), mean corpuscular volume (MCV), mean corpuscular hemoglobin (MCH) and mean corpuscular hemoglobin concentration (MCHC) to be assessed at a local laboratory.⁶ Includes ALT, AST, ALP, BUN or urea, uric acid, creatinine, total bilirubin and glucose to be assessed at a local laboratory.⁷ Urine dipstick, followed by microscopy if abnormal to be assessed at a local laboratory.⁸ Investigator's efficacy assessment and review of subject's diary including infusions, bleeding summary, subject's efficacy assessment, adverse events and concomitant medications. At Screening, review of subject diary to include review of previous factor IX therapy (if available).⁹ Inhibitory and non-inhibitory factor IX antibodies to be assessed by central lab at PK Phase Pre-infusion for subjects weighing ≥ 28 kg, and all subjects at all other time points.¹⁰ Factor IX mutation assessment to include mutation genotyping by central laboratory if not previously documented. For patients below 10 kg this may be done

at any time during the study when blood volumes allow

¹¹ Factor IX activity to be assessed by central lab pre-infusion and post-infusion at 15-30 minutes, 4-6 hours, 24-26 hours, and 46-50 hours. Pre-infusion and 15 to 30 minutes post-infusion samples will be tested for factor IX activity to determine the starting prophylaxis dose. See protocol section 5.7.1 for further details.

¹² Screening to occur 21 to 5 days prior to PK phase.

¹³ CD4 count to be assessed by local laboratory.

¹⁴ See protocol Table 2 for thrombogenicity assessments by subject weight; thrombogenicity markers include D-dimer, TAT complex, fragment 1+2.

¹⁵ For patients below 17 kg, CBC with differential and serum chemistry should be collected if blood volumes allow.

¹⁶ Anti-CHOP antibodies to be assessed by central laboratory at PK phase pre-infusion for subjects weighing ≥ 28 kg

Table 1: Thrombogenicity Assessments During PK Phase by Subject Weight

Subject weight	Pre-infusion	15-30 min post-infusion	4-6 hours post-infusion	24-26 hours post-infusion
≥ 20 kg	X	X	X	X
≥ 17 kg to <20 kg	X	X		X
<17 kg ¹				

¹ To accommodate blood volume limitations for subjects <17 kg, no thrombogenicity assessments will be performed during the PK Phase. Thrombogenicity assessments may be drawn at these timepoints during the Treatment Phase when blood volume limitations allow.

Table 2: Schedule of Events for a Surgical Procedure (if required during Treatment Phase and/or Continuation Phase)

Evaluations	Prior to surgery ¹		During surgery	End of surgery	12 hours post-surgery		24 hours post-surgery ²		28 days (± 7 days) post-factor IX replacement therapy for surgery
	Pre-infusion	Post-infusion (5-30 min)			Pre-infusion	Post-infusion (5-30 min)	Pre-infusion	Post-infusion (5-30 min)	
Factor IX activity ³	X	X	X ⁴		X	X	X	X	
Vital signs	X				X		X		
Adverse events		X	X	X		X		X	

Evaluations	Prior to surgery¹		During surgery	End of surgery	12 hours post-surgery		24 hours post-surgery²		28 days (± 7 days) post-factor IX replacement therapy for surgery
	Pre-infusion	Post-infusion (5-30 min)			Pre-infusion	Post-infusion (5-30 min)	Pre-infusion	Post-infusion (5-30 min)	
Use of blood products			X	X	X		X		X
Surgeon's assessment of expected/estimated blood loss	X			X	X		X		

¹ If using bolus infusions, an infusion of up to 120 IU/kg will be given within 1 hour prior to the start of the procedure, followed by an infusion of approximately 60 IU/kg 12 hours after the first infusion and an infusion of up to 120 IU/kg 24 hours after the first infusion. If administering a continuous infusion, the plasma factor IX activity should range between 70% and 110%, and the dose and timing of subsequent infusions and adjustments should be recorded and guided by factor IX activity results.

² Continue with bolus or continuous infusion treatment for as long as the surgeon deems necessary, but for a minimum of 3 days post-surgery for major surgery or a minimum of 1 day post-procedure for minor surgery. Assess pre- and post-infusion factor IX activity every 12 hours.

³ Factor IX activity is to be assessed by the local laboratory at all time points. If blood volumes allow, factor IX samples should also be assessed by the central laboratory.

⁴ If study product is infused during surgery, measure factor IX activity pre- and post-infusion (5-30 minutes).
